During the session participants will be exposed, in random order, to sweet (watermelon e-liquid) with and without menthol, in a 36mg/ml nicotine salt, as nicotine salt is currently the most common and popular nicotine formulation among young adult e-cigarette users. Each of the two exposures will consist of a single fixed-puff bout (10 puffs; each 3-sec duration, with a 30-sec inter-puff interval). These procedures were adapted from our recent work ²⁶ where we used three puff bouts to achieve sufficient and sustained increases in nicotine levels, to conduct an adequate test of nicotine exposure on outcomes of interest. As we are not examining withdrawal and craving, a single puff bout should be sufficient to capture this. Each exposure will be separated 30 minutes to allow flavor sensation to dissipate as well as give time for nicotine effects to reduce. Prior to testing, subjects will be familiarized with the sensory and hedonic rating scales.²⁷⁻³¹ Cotinine and CO levels will be used to confirm nicotine/tobacco non-use status. After each exposure, participants will rate the flavor intensity, coolness, sweetness, and irritation (burning, stinging) experienced using the generalized Labeled Magnitude Scale (gLMS)^{31,32}, and liking/disliking of the flavor sensation using the Labeled Hedonic Scale (LHS)²⁷. These procedures are adapted from our earlier work ². Follow ups: Participants will be contacted at 1-month time-points to determine changes in use of e-cigs (with and without nicotine), any health changes, and other tobacco use (number of days used/30 days) using Timeline Follow-Back methods³³⁻³⁷. We will examine whether the sensory attributes of

different flavors observed in the experimental session predicts use of nicotine-containing e-cigs, or preference for flavors, during the follow-up periods.

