Study 2: Examine if flavors differentially influence reward from nicotine-containing e-cigs and e-cig use behaviors among younger and older adult combustible tobacco users. 120 cigarette smokers (60 young adult users; 60 older adult users) will be randomized into one of two nicotine-concentration groups (6 or 18 mg/ml); Sex (male, female) and use of mentholated tobacco products (yes, no) will be stratifying factors. Within each nicotine condition (6 or 18 mg/ml), participants will receive, in counterbalanced order, each of four flavors (tobacco, menthol, cherry and vanilla) during four different laboratory sessions separated by at least 24 hrs.

Nicotine		Flavors (Within Ss Factor)			
(Between Ss Factor)		Tobacco	Menthol	Vanilla	Cherry
6 mg/ml		S ₁ -S ₆₀			
18 mg/ml		S ₇₀ -S ₁₂₀			

Set up and baseline assessments	Puff Bouts					End of lab assessments
	10 Puffs	Break	10 Puffs	Break	10 Puffs	
15 mins	5min	10 min	5min	10 min	5min	15 minutes

Participants will be required to be abstinent from cigarettes for 12 hrs. (CO level <9 ppm) prior to each session, which will consist of 3 fixed-puffing bouts (10 puffs; each 3-sec duration, with a 30-sec inter-puff interval); each fixed-puff bout will be separated by 10 min (see Table above). These

procedures were adapted from our recent work ²⁶ where we used three puff bouts to achieve sufficient and sustained increases in nicotine levels, to conduct an adequate test of nicotine exposure on outcomes of interest. Per our current practice, we will record timed instructions for each puffing bout and participants will be trained to follow these directions. Nicotine/cotinine levels will be monitored using saliva samples obtained at baseline and then at the end of each puff bout. Prior to testing, participants will be familiarized with the assessments and trained in how to puff e-cigs. Training will be conducted using e-cigs that contain the base liquid of 50% propylene glycol/50% vegetable glycerin.

The Revised Drug Effects Questionnaire (DEQ; e-cig liking/wanting, nicotine withdrawal, and stimulation) ², Multiple Choice Questionnaire (MCQ; e-cig value) ³ will be assessed after each 10-puff exposure period (see below for the list of assessments).

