4. Multiple Choice Questionnaire to assess e-cig value (Adapted from Multiple Choice Procedure (MCP)^{3,26} (Study 1, Study 2): At the end of each fixed-10-puff period, participants will be asked to make discrete hypothetical choices between 10-puffs of the e-cig they had just used or a series of 44 monetary values (\$0.25-\$15.06). The minimum monetary value at which money is chosen over the e-cig puffs is a contingency-based estimate of e-cig value. At the end of each lab session, participants will be given a choice between another 10 e-cig puffs or one of the monetary amounts they picked in the MCPs completed earlier.

5. Asthma Control Test⁴⁰ (Study 1, Study 2): At intake, at every in-person visit, and at follow up appointments, participants will be asked to rate their asthma symptoms on a 1-5 scale, from "all of the time" to "none of the time". This five-question health survey is used to measure asthma control in individuals 12 years and older

6. Fatigue⁴¹ (Study 1, Study 2): At intake, at every in-person visit, and at follow up appointments, we will use the 7-item PROMIS measure of fatigue which rates fatigue from 1="never" to 5="always".

7. Shortness of Breath (Study 1, Study 2): At intake, at every in-person visit, and at follow up appointments, we will use the 5-item PROMIS measure of dyspnea which rates shortness of breath from 1-10. Items include: shortness of breath in general, intensity of shortness of breath, frequency of shortness of breath and duration of shortness of breath.

8. Carbon Monoxide (CO) levels (Study 1, Study 2): CO levels in exhaled breath will be measured using a MicroCO breath CO monitor and levels of < 6 ppm will be used to ensure abstinence prior to the lab sessions, *during the 2-week ad-libitum use period [ad lib portion ON HOLD]* (Study 2), and at the follow-ups (Study 1).

9. Urine Cotinine levels (Study 1, Study 2): Cotinine levels are accurate indicators of tobacco use even among adolescents^{42,43} Urine samples will be obtained at intake to verify eligibility for Study 1 and 2 and prior to the start of each laboratory session. *We will also assess cotinine levels once a week during the ad-lib session of Study 2 [ad lib portion ON HOLD].* Cotinine levels will be determined using LC/MS by the YCSTP core laboratory.

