Participants in Study 2 will receive \$50 for Intake and \$25 for in-person intake. If ineligible after intake, participants will receive compensation in the form of an electronic gift card of their choosing (examples include but are not limited to Amazon, Wal-Mart, Target, Stop & Shop). If they do not have an email account, a gift card will be mailed to them. Participants in Study 2 (n=120) will receive escalating payments per lab session to increase completion (\$50 for Lab 1, \$75 for Lab 2, \$100 for Lab 3, \$125 for Lab 4) and a \$25 gift card for each of the follow up visits (1 month, 6 month).

Both studies will compensate participants \$20/day for travel to appointments after the initial intake (up to \$100, follow ups will conducted over the phone). Thus, each participant in Study 1 can earn a total of \$215 (including value of gift cards) and each participant in Study 2 can earn up to \$575 (including value of gift cards). If participants have borrowed a study cell phone from us for the study, we will ask that they return the cell phone at the last visit. The final visit payment will be withheld until the cell phone is returned. Participants enrolled in the study will be paid via cash or in some cases (see above) gift cards. As the ad-lib portion of Study 2 is on hold, participants will not receive payments associated with the ad-lib portion of the study (i.e. compensation for daily CosCOs, questionnaires, ad-lib visits, as well as returning the e-cigarette and battery).

Participants may earn a \$25 referral bonus for each friend that is referred to participate in this study. In order to receive this bonus, the friend(s) must complete the intake appointment and physical exam.

We will validate parking in the Air Rights parking garage. We will provide round trip cab transportation to appointments after the remote intake, if transportation is an issue.

3. **Costs for Participation (Economic Considerations):** Clearly describe the subject's costs associated with participation in the research, and the interventions or procedures of the study that will be provided at no cost to subjects.
There are no costs for participation.
4. **In Case of Injury:** This section is required for any research involving more than minimal risk, and for minimal risk research that presents the potential for physical harm (e.g., research involving blood draws).
 - a. Will medical treatment be available if research-related injury occurs? *Write here*

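### As written, the session-end payout of the Multiple Choice Questionnaire rewards overstating e-cig value, which conflicts with calling this Study 2 secondary outcome contingency-based

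*Combined protocol and SAP*

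**What the plan says.** The task is item 4 of the Assessments list in Section I.4 (Research Plan) and is assigned to both studies. It is given after every bout of 10 puffs, and the plan states that "participants will be asked to make discrete hypothetical choices between 10-puffs of the e-cig they had just used or a series of 44 monetary values", running from $0.25 to $15.06. The score is defined next: "The minimum monetary value at which money is chosen over the e-cig puffs is a contingency-based estimate of e-cig value". The item ends with the payout, made at the close of each session, where the text reads: "participants will be given a choice between another 10 e-cig puffs or one of the monetary amounts they picked in the MCPs completed earlier".

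The item does not say how the one amount is selected, what is offered to someone who never picked money, or what participants are told about the payout. On preparation, the Study 2 description says "participants will be familiarized with the assessments and trained in how to puff e-cigs". The Study 1 description says only that "subjects will be familiarized with the sensory and hedonic rating scales".

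E-cig value belongs to the Study 2 secondary aim (Section I.1) and is analyzed as a secondary/exploratory outcome by mixed model (Section I.13, Aim 2). The Study 1 analysis paragraph does not list it. Section VI.2 gives maximum payments of $215 (Study 1) and $575 (Study 2) and does not mention money from this questionnaire.

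**The concern.** A choice procedure measures value when the answer on each item has a consequence: someone who claims to prefer puffs to $5 risks getting the puffs and not the $5. Here that link is missing. Items answered with puffs never enter the payout, and the final choice is made afresh. The answers decide only which sums of money can be offered, and refusing small sums removes them from that set. A participant who values the puffs at $1 does best by picking money only at $15.06, whatever the flavor.

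If participants act on this, reports move toward the top of the list. Flavor, dose and age contrasts in e-cig value then shrink, because reports held at a common ceiling cannot differ. The item also describes the choices as hypothetical and the score as contingency-based, and the payout as written is consistent with neither.

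**Working it through.** **1. The plan's own figures.** There is no design figure for this outcome. The Study 2 power of 82% reproduces (f = 0.4, 54 participants at 18 mg/ml, noncentrality 0.16 × 54 = 8.64, 1 and 52 df: 0.822), but it is for liking/wanting and does not bear on this point. The payment totals reproduce with no questionnaire money in them:
- Study 1: 50 + 100 + 25 + 40 = $215.
- Study 2: 50 + 25 + (50 + 75 + 100 + 125) + 2 × 25 + 100 = $575.
- Money the payout could add: $15.06 per session, so up to $15.06 in Study 1 and 4 × 15.06 = $60.24 in Study 2.

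**2. The price list.** The plan gives the count and the end points but not the spacing. Steps of 10% fit exactly (0.25 × 1.1^43 = 15.06). Equal steps were tried as well.

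**3. Payoff under the rule as written.** Let v be the true value of the puffs and c the stated crossover. The offer m is one of the amounts at or above c, and the participant takes the better of m and v. With a random draw (assumed), the payoff is the mean of max(m, v) over m ≥ c. Raising c deletes the smallest amounts from that mean, so the payoff cannot fall, for any v and any spacing. Mean offer with 10% steps:

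| Stated switch | Amounts picked | Mean offer |
|---|---|---|
| $1 | 29 | $5.35 |
| $5 | 12 | $9.41 |
| $10 | 5 | $12.56 |
| top item | 1 | $15.06 |

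Going from $1 to the top multiplies the offer by 15.06 / 5.35 = 2.8. For v = $3 the payoff for a truthful report, a doubled report and a top report is $7.82, $10.18 and $15.06 with 10% steps, and $9.03, $10.58 and $15.06 with equal steps. If the lowest picked amount were offered instead, the direction is the same ($1.04 to $15.06 in the first example). If the highest were always offered, overstating would gain nothing but would still cost nothing. Never picking money is the one undefined case.

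**4. Comparison rule.** Draw one of the 44 choices and honor it as made. The payoff is the mean over all 44 items of m where money was chosen and v where puffs were chosen. For v = $3 and equal steps, a truthful report gives $7.94, a doubled report $7.65 and a top report $3.27. Truthful reporting was best in every case tried (v = $1, $3, $6, $10; both spacings).

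**5. What it could do to a contrast (illustration).** Assume true means of $3.00 and $4.50 for two flavors, and a share p of participants who report $15.06 for both. The expected difference is (1 − p) × 1.50. For power, take a within-subject contrast with 80% power at n = 108 and alpha 0.05, so d = (1.960 + 0.842)/√108 = 0.270. With a difference of zero for the share p, the mean is (1 − p)d, the variance is (1 − p)(1 + d²) − (1 − p)²d², and power is Φ(mean × √108 / SD − 1.960).

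| p | Means | Difference | Power |
|---|---|---|---|
| 0 | $3.00, $4.50 | $1.50 | 80% |
| 10% | $4.21, $5.56 | $1.35 | 75% |
| 25% | $6.02, $7.14 | $1.12 (0.75 × 1.50 = 1.125) | 67% |
| 50% | $9.03, $9.78 | $0.75 | 49% |

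**6. Opportunity to learn the rule.** Study 2 has 4 sessions of 3 bouts, so 12 questionnaires, of which 9 come after the first payout. Study 1 has a single session, and its only payout follows both questionnaires.

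**The case against.** The strongest reply is that an incentive is not a bias. The items are presented as hypothetical, nothing says participants are told the payout rule, and the item is a short summary of a cited procedure that may specify the draw more fully. The cash ratios in step 3 describe offers, not flavor contrasts, and the shares in step 5 are assumed. All of this stands, and it limits what can be claimed. It does not remove the conflict in the text: the rule that is stated restricts the offer to picked amounts and reopens the choice, and that does not support the contingency-based label. If the intent is to honor an earlier choice, the sentence needs correcting anyway.

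Several stronger readings are tempting and are not supported:
- **That e-cig value is pushed upward and its contrasts compressed as a matter of fact.** This needs participants to know or learn the rule, and a constant dollar shift in every flavor would leave differences unchanged.
- **That drift over sessions confounds flavor.** Flavor order is counterbalanced (Section I.4, Study 2) and the model includes measurement time (Section I.13), so uniform drift is handled. Attenuation at the ceiling is what remains.
- **That this is the only behavioral measure, or that value loses all meaning.** The session-end choice is itself behavior, Study 1 analyzes later e-cig use, and ad-lib consumption is planned though on hold.
- **That the payment totals show distortion.** They show an accounting omission only.

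**Conclusion.** The payout as written is not incentive-compatible. Overstating e-cig value carries no cost, and it raises the cash offer under a random or lowest-amount draw. This follows from the wording for any spacing of the list and any true value. The conflict with the contingency-based label, and the omission of this money from the $215 and $575 maxima, hold however participants behave.

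The effect on results is conditional. It is plausible in Study 2, where the rule can be learned over four sessions, and it would take the form of attenuated flavor, dose and age contrasts in e-cig value. Its size cannot be derived from the documents. The $1.35 to $1.12 range for a true $1.50 difference rests on an assumed 10% to 25% of participants at the ceiling. Primary liking/wanting and its stated power are untouched. Study 1 is little exposed. The point is worth correcting because the outcome serves a stated secondary aim and the correction is cheap.

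**What to change.** Replace the last sentence of Assessments item 4. At the end of each session one item is drawn at random from all choices made in that session, and the participant receives what was chosen on it, the sum or the puffs. Participants are told this before the first questionnaire. They remain free to decline or stop puffing, as Section I.10 already allows, but declined puffs are not exchanged for money, since that would bring the incentive back. Remove the description of the choices as hypothetical.

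The alternative is to keep the task hypothetical, delete the session-end choice and the contingency-based label, and limit the conclusion to hypothetical value.

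Under either option, apply the change only to participants who have not started lab sessions, so that no one's flavor sessions fall under two rules. Include rule version as a between-subject term in the e-cig value model. For data collected under the present rule, tabulate the share of reports at $15.06 by session and flavor. In Section VI.2, reconcile the stated maxima with any questionnaire money (up to $15.06 per session).

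The cost is small changes to protocol, consent and payment wording, a random draw at session end, and a version indicator. The sums at risk are no larger than those the present rule can already pay. If few participants remain to be started, the rule change will help little and the limit on interpretation becomes the main remedy.

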7. **Subject classification:** Check off all classifications of subjects that will be specifically recruited for enrollment in the research project. Will subjects who may require additional safeguards or other considerations be enrolled in the study? If so, identify the population of subjects requiring special safeguards and provide a justification for their involvement.

 Children	 Healthy	 Fetal material, placenta, or dead fetus
 Non-English Speaking persons	 Prisoners	 Economically disadvantaged
 Decisionally Impaired	 Employees	 Pregnant women and/or fetuses
 Yale Students	 Females of childbearing potential	

NOTE: Is this research proposal designed to enroll children who are wards of the state as potential subjects?

Yes **No**

8. **Inclusion/Exclusion Criteria:** What are the criteria used to determine subject inclusion or exclusion?

Study 1:

Inclusion Criteria:

- (1) Ages 18-20
- (2) Able to read and write
- (3) Have used e-cigs at least 10 times in lifetime
- (4) Have used flavored e-cigs
- (5) Have used e-cigs in the past 30 days
- (6) Cotinine level >200 ng/ml (indicating recent cotinine use)

Exclusion Criteria:

- (1) Current criteria for moderate or severe cannabis and alcohol use disorder as per DSM-V criteria.
- (2) Current criteria for mild, moderate or severe substance use disorder on any other psychoactive substances as per DSM-V criteria except for tobacco use disorder
- (3) Use of psychoactive drugs including anxiolytics, antidepressants, and other psychostimulants unless prescribed and stable for two months
- (4) Current diagnosis of any severe psychiatric disorder.
- (5) Any significant current medical condition such as neurological, cardiovascular, endocrine, renal, or hepatic pathology that would increase risk or would interfere with/mimic tobacco abstinence
- (6) Known hypersensitivity to propylene glycol.
- (7) Pregnant or lactating females.
- (8) Uncontrolled asthma (defined as <20 on Asthma Control Test AND/OR endorsement of "yes" to environmentally induced bronchospasm that requires prescription Epipen

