- (9) Medical conditions, including chronic and untreated acute pulmonary conditions, that in the investigators view will increase risk of respiratory problems among participants
- (10) Nut allergy or known allergy to e-liquids and/or their flavorants
- (11) Report of greater than "without any difficulty" on any item of the PROMIS Physical Function Short Form
- (14) For current THC vapers: Any report of mild or great EVALI-related symptoms (i.e. cough, shortness of breath, chest pain, nausea, vomiting, stomach pain, diarrhea, fever, chills, or weight loss) without non-EVALI reasonable and proximal cause
- (15) Not fully vaccinated against COVID-19

Study 2:

Inclusion Criteria:

- (1) Ages 21--50 years

- (2) Able to read and write
- (3) Smoking cigarettes or cigars daily for at least the past 30 days (month)
- (4) urine cotinine levels of at least 200ng/mL
- (5) Willing to abstain from regular smoking for 2 weeks and use only e-cigs [Ad-lib portion of the study on hold; this inclusion criteria is ON HOLD until ad lib portion is resumed]
- (6) Not seeking treatment to stop smoking
- (7) Use of e-cigarettes at least 10 times in the past six months
- (8) Do not plan to discontinue e-cigarette use
- (9) Have not stopped use due to COVID
- (10) Do not have a strong preference for a flavor or a device

Exclusion Criteria:

- (1) Current criteria for moderate or severe cannabis and alcohol use disorder as per DSM-V criteria.
- (2) Current criteria for mild, moderate or severe substance use disorder on any other psychoactive substances as per DSM-V criteria except for tobacco use disorder
- (3) Use of psychoactive drugs including anxiolytics, antidepressants, and other psychostimulants unless prescribed and stable for two months
- (4) Current diagnosis of any severe psychiatric disorder.
- (5) Any significant current medical condition such as neurological, cardiovascular, endocrine, renal, or hepatic pathology that would increase risk or would interfere with/mimic tobacco abstinence
- (6) Known hypersensitivity to propylene glycol.
- (7) Pregnant or lactating females.
- (8) Uncontrolled asthma (defined as <20 on Asthma Control Test AND/OR endorsement of "yes" to environmentally induced bronchospasm that requires prescription Epipen)
- (9) Medical conditions, including chronic and untreated acute pulmonary conditions, that in the investigators view will increase risk of respiratory problems among participants

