told that if they do not feel comfortable with this, then they should not participate in the project. They will also be told that if they report any information to us about abuse or homicidal/suicidal behavior, we will be required to report this information to the appropriate authorities.

11. Minimizing Risks: Describe the manner in which the above-mentioned risks will be minimized.

Recruitment and Informed Consent Recruitment for Study 1 will be conducted via a variety of methods. We will utilize Craigslist, flyers, Reddit, and social media to recruit. All participants recruited via Craigslist, flyers, Reddit, and social media will be referred to ongoing cessation studies or given cessation materials at the end of the current study.

Recruitment for Study 2 will be through advertisements on Craigslist, Facebook, flyers in the community, radio and novelties (e.g. matchbooks, bottle openers, tic tacs, coasters, etc). At the initial intake session, potential participants will sign informed consent and complete initial assessments. As in Study 1, medical and substance abuse histories, urine drug and pregnancy tests, breath CO and urine cotinine levels will be obtained from all participants. All participants will receive an extensive medical history evaluation reviewed by the study APRN and a psychological evaluation to determine eligibility. If all the study criteria are met and consent is obtained, the research assistant will work with the participant to set up the experimental schedule.

12. Data and Safety Monitoring Plan: Include an appropriate Data and Safety Monitoring Plan

(DSMP) based on the investigator's risk assessment stated below. (Note: the HIC will make the final determination of the risk to subjects.)

- a. What is the investigator's assessment of the overall risk level for subjects participating in this study? Greater than minimal risk
- b. If children are involved, what is the investigator's assessment of the overall risk level for the children participating in this study? Minor increase over minimal risk

This study presents greater than minimal risk given that we will be providing participants with an electronic cigarette in a lab. However, we will reduce risk by:

- Obtaining consent from ≥ 18 year old's
- Requiring experience with e-cigs.
- Using well-defined inclusion/exclusion criteria and physical exams and clinical psychological evaluations to rule pre-existing medical conditions.

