Statistical analyses: Preliminary analyses will provide an overview of the data (e.g., randomization success, outcome distribution, missingness patterns). Outcome analyses will be intent-to-treat and using mixed-effects models. These models allow for different numbers of observations per subject, use all available data, and can handle missing-at-random data. If model assumptions will appear to be violated, we will transform the data or fit more flexible generalized linear or nonparametric mixed models. A significance level of 0.05 will be used for primary outcomes and a Bonferroni correction will be applied for secondary outcomes.

Aim 1 (Study 1). Mixed-effects model will include menthol (yes, no), and measurement time (lab, time-within-lab). A combination of random effects and structured variance-covariance matrices will be used to account for within-subject correlations. The best-fitting structure will be selected based on Akaike information criterion (AIC). We also anticipate statistically significant main effects of menthol on liking. Similar models will be used for the secondary outcomes (flavor intensity, coolness, sweetness and harshness). Mixed models will be used to test whether menthol-related alleviation in harshness and improvement in liking (subject-specific difference between menthol and no-menthol scores) predicts percent days of nicotine-containing e-cig use at 1-month and follow up.

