Appendix

Psychological Evaluation: Standard Operating Procedure

Relevant eligibility criteria to be assessed by psychological evaluation:

1. Current criteria for moderate or severe cannabis or alcohol use disorder as per DSM-V criteria
2. Current criteria for mild moderate or severe substance use disorder on any other psychoactive substances as per DSM-V criteria except for tobacco use disorder.
3. Use of psychoactive drugs including anxiolytics, antidepressants, and other psychostimulants unless prescribed and stable for two months
4. Current diagnoses of any severe psychiatric disorder.

Introduction:

- Introduce yourself to participant (if applicable), explain the purpose of this portion of the intake (to assess brief mental health and substance use history to assess participant's psychiatric health history and safety before participating in our study).
- Note that you will ask some questions that are sensitive about drug, alcohol, and psychiatric history, but all information will be kept confidential and only shared with team members as necessary for the study
- Capture current living situation (e.g., with whom and where) and employment (document on Psychological Evaluation Form).
- Ask participants hobbies, other activities they do outside of employment, family life.

For Substance Use eligibility criteria (1 & 2):

- Collect tobacco use history, including what products they use. For each product, obtain age of initiation, current use frequency, products currently used, desire to quit, past quit experience [e.g., when, for how long]). Document on Psychological Evaluation Form.
- Assess ever use of alcohol, cannabis, stimulants, opioids, inhalants, PCP, hallucinogens, other substance.
- Collect details of ever self-reported drug and alcohol use (age of initiation, quantity, frequency, most recent use, any current use). Document on Psychological Evaluation Form.
- If past 12 month use of any of the above, assess presence and severity of SUD using SCID-RV (for DSM-5).
- If applicable, following eval, confirm with Research Assistant conducting the intake that self-report of substance use matches the medical history reported.

For Psychiatric criteria (3 & 4):

- Ask participant for a brief mental health history. Specifically obtain any diagnoses, both formal or informal, length of symptoms, treatment(s) if any, and any current symptoms of psychiatric conditions.

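### Study 1 has no counterpart to Study 2's rule on plans to stop e-cigarettes, so young vapers about to quit can enrol and dilute the exploratory one-month association

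*Combined protocol and SAP*

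**What the plan says.** All references are to the combined protocol and SAP.

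- **Section I.8, Study 1.** The six inclusion criteria cover age, literacy, lifetime use ("Have used e-cigs at least 10 times in lifetime"), use of flavored products, recent use ("Have used e-cigs in the past 30 days") and nicotine exposure ("Cotinine level >200 ng/ml (indicating recent cotinine use"). Neither these nor the Study 1 exclusions mention quitting, cessation treatment or plans to stop.
- **Section I.8, Study 2.** Item 6 reads "Not seeking treatment to stop smoking" and item 8 reads "Do not plan to discontinue e-cigarette use". Section I.6 repeats the contrast: only the Study 2 population is described as not seeking to quit.
- **Section I.4, Study 1B.** Each participant has two 10-puff exposures at 36 mg/ml nicotine salt, then a one-month contact about use.
- **Section I.13, Aim 1.** Mixed models test whether the menthol versus no-menthol difference in harshness and liking "predicts percent days of nicotine-containing e-cig use at 1-month and follow up". No adjustment for quit intention or baseline use is named. Section I.1 labels the one-month question exploratory.
- **Section I.11.** Study 1 recruits "will be referred to ongoing cessation studies or given cessation materials at the end of the current study". The Safety Monitoring Plan in I.12 gives cessation resources to every Study 1B participant at the end of the lab session.
- **Appendix, psychological evaluation procedure.** For each tobacco product it records "current use frequency, products currently used, desire to quit, past quit experience". The eligibility criteria listed there do not use the answer.

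**The concern.** Study 1 recruits its participants as vapers, gives them nicotine, and then takes vaping as a follow-up outcome. Whether someone already intends to stop bears directly on that outcome, yet the only e-cigarette intention rule sits in the other study. Someone in the early stage of a quit attempt can meet every Study 1 criterion.

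Two things are at stake. First, enrolment: whether such a person should take part is a decision for the investigators, and the protocol appears to decide it differently in the two studies without saying why. Second, analysis: quitting lowers one-month use for a reason that need have nothing to do with menthol. With about 36 people, a few such values can obscure a real relation.

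**Working it through.** **1. Do the existing Study 1 criteria close the gap?** Only in part. The cotinine threshold removes people who have already stopped all nicotine. It shows recent exposure, not an intention to continue, and past-30-day use is equally silent on plans. The remaining group is people planning or just starting to stop.

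**2. Which analysis is touched?** The menthol contrast on liking compares each person with themselves within one session, so a stable characteristic such as quit intention cancels. The one-month analysis compares people with one another, so quit intention enters the residual.

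**3. How large could the effect be?** The plan states no power for the one-month analysis, so there is no figure to reproduce. From Section I.13, 40 recruited less 10% dropout gives n = 40 × 0.9 = 36. Everything else here is assumed: a true correlation r = 0.45 in non-quitters, a two-sided 5% test, and a share q of quitters unrelated to liking.

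*Starting point.* Power ≈ Φ(atanh(r)·√(n − 3) − 1.96). With r = 0.45, this is 0.4847 × 5.745 − 1.96 = 0.824, so power is about 79%. At n = 36, r of about 0.45 is also the correlation detectable with 80% power.

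*Quitters use D standard deviations less but keep the slope.* Observed r = 0.45 / √(1 + q(1 − q)D²).
- D = 1: r = 0.431, 0.418, 0.409 at q = 10, 20, 30%; power 76%, 73%, 70%.
- D = 2: r = 0.386, 0.351, 0.332; power 65%, 56%, 51%.

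*Quitters have no slope and half the spread.* Observed r = (1 − q)·0.45 / √((1 − q) + 0.25q + q(1 − q)D²).
- D = 1: r = 0.402, 0.358, 0.317; power 69%, 58%, 47%.
- D = 2: r = 0.357, 0.295, 0.248; power 57%, 42%, 31%.

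*Simulation on the bounded outcome.* Percent days of use is limited to 0–100, with assumed mean 70 and SD 25 in non-quitters. Simulation error is about one percentage point.

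| Assumed behavior of quitters | 10% | 20% | 30% |
|---|---|---|---|
| Mean 57.5, slope kept | 77–78% | 77–78% | 77–78% |
| Mean 45, slope kept | 75% | 72% | 71% |
| Mean 45, SD 25, no slope | 64% | 50% | 38% |
| Mean 10, SD 10, no slope | 51% | 35% | 25% |

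In the last row the mean observed correlation falls from 0.44 to 0.33, 0.25 and 0.21. If the true correlation is 0.3, power is only about 42% with no quitters at all.

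**4. Would adjustment help?** In the last-row scenario, adding actual quit status to the model gives power of about 73%, 66% and 59%. Stated intention is an imperfect marker of actual quitting and would recover less.

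**The case against.** The strongest reply is that this touches only an exploratory question for which no power is claimed, while the primary contrast is sound. That stands, and it limits the weight of the point. The lowest powers also come from the harshest assumption, near-complete stopping regardless of liking. With milder assumptions the loss is a few percentage points.

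The Study 2 comparison can be overread. Item 6 concerns smoking, so item 8 is the direct counterpart. Study 2 was designed with a two-week switch to e-cigarettes, now on hold, which gives its rules an evident design role. A reader might infer that they exist to protect people trying to quit, and that Study 1 strips this protection from those most at risk. The documents state no such purpose and give no figure ranking harm. Study 1 participants may stop at any time and all receive cessation resources. A reader might also infer that nicotine replacement supplies the required cotinine in some recruits. The criteria do not rule that out, but nothing in the documents shows that it happens.

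Finally, the entry rule cannot prevent quitting prompted by the cessation resources, which are given out before the one-month contact. That also stands. None of this explains why the intention rule is in one study and not the other.

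**Conclusion.** The omission is confirmed, and the difference between the studies is unexplained. Its statistical effect is confined to the exploratory one-month association. Provided quitting is unrelated to the menthol difference in liking or harshness, the effect is attenuation, not a spurious finding. Its size cannot be fixed from the documents: under the assumptions above, power falls from about 79% to anywhere between 78% and 25%, depending on how many participants quit and how completely.

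A reader might take the lower end as the expected loss, or conclude that Study 1's main result is compromised. Neither is supported: the lower end rests on assumed near-total stopping, and the primary contrast is within person. This is a low-cost improvement, not a flaw that threatens the study's main conclusion.

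**What to change.** - **Reconcile the criteria.** Either carry Study 2 item 8 into the Study 1 inclusion list or state why it does not apply. The choice is the investigators'.
- **Ask directly at intake** about current plans to stop e-cigarettes and about seeking treatment. The evaluation item on wishing to quit is broader than a plan and could exclude many more people. It is also unclear whether Study 1 uses that procedure: Section I.12 describes a psychological evaluation for participants generally, Section I.9 lists none for Study 1B, and the file path in the Appendix names Study 2.
- **Prespecify two covariates in the one-month model:** quit intention at intake, and baseline use from the 30-day Timeline Follow-Back already collected at Study 1 intake (Section I.4, additional assessments). For anyone already enrolled without the direct question, baseline use is still available.

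The cost is one or two intake questions, somewhat slower recruitment, a population limited to young vapers with no current plan to stop, and one or two model degrees of freedom. Quitting prompted by the end-of-session cessation materials will remain and should be acknowledged when the one-month result is interpreted.
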